Study Phase 2: Assess the efficacy of motivational interviewing plus the WHEELS-I program vs. motivational interviewing alone in promoting adoption of the DASH/SRD. Determine the effects of DASH/SRD adoption over a 6-month period on structural cardiovascular HFpEF risk factors in salt sensitive vs. salt-resistant veterans.

*Introduction:* Structural correlates of HFpEF include left ventricular hypertrophy, which strongly predicts HF onset in older adults, left atrial enlargement, which reflects chronically elevated ventricular filling pressures, and stiff central arteries. No previous studies in participants with HTN and metabolic syndrome have examined the relationship between the salt-sensitive phenotype and these HFpEF risk factors after long-term dietary

modification. Current guidelines recommend the DASH/SRD to prevent cardiovascular disease in hypertensives with metabolic syndrome, but adherence to this dietary pattern is declining nationwide. Our working hypotheses are that: 1) When compared to motivational interviewing alone, the addition of the Women's and Men's Hypertension Experiences and Emerging Lifestyles Intervention (WHEELS-I) program, an electronically-delivered tailored messaging intervention, will improve adoption of the DASH/SRD over a six month period, and 2) sustained adoption of the DASH/SRD over 6 months will produce greater improvement in structural cardiovascular HFpEF risk factors in salt-sensitive than salt-resistant subjects, with measures including left ventricular mass index (LVMI, primary outcome), left atrial volume index (LAVI), cfPWV, and BP.

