[figure not shown]
Dietary Prevention of Heart Failure in Hypertensive Metabolic Syndrome

NCT03170375

May 31, 2025

Statistical Plan

The study was conducted in two phases. *Phase 1* evaluated the salt-sensitivity of blood pressure, with 2 weeks of ad-lib diet followed by 2 weeks of provided sodium-restricted Dietary Approaches to Stop Hypertension (DASH/SRD) meals, with outcomes assessed at 2 and 4 weeks of study participation. *Phase 2* evaluated the efficacy of motivational interviewing-based dietary counseling, with or without the Women's and men's Hypertension Experiences and Emerging LifestyleS (WHEELS) mobile application, with outcomes assessed from baseline to the end of the study. The study schematic is shown below, along with data collection and the flow of participants that were still actively participating at key timepoints.

The primary outcome of *Phase 1* was the change in carotid-femoral pulse wave velocity (PWV), with secondary outcome of the change in left ventricular global longitudinal strain by echocardiography, between week 2 and week 4 of study participation. Since *Phase 1* of the study occurred prior to randomization, the comparator groups are salt-sensitive and non salt-sensitive individuals, with blood pressure salt-sensitivity defined as a reduction in mean arterial pressure by 24-hour ambulatory monitoring in week 4 (DASH/SRD diet period) compared to week 2 (ad-lib diet period). *Phase 1* outcomes were analyzed using linear regression adjusted for baseline value.

Sample size was based on a 2-sequence, 2-period, 2-treatment crossover design for continuous endpoints (using paired t test for mean differences). We assumed a within-subject correlation of 0.70 for PWV measurements, based on our preliminary data and the literature and assumed a 10% dropout rate during *Phase 1* of our study. Under these assumptions and using a two-sided type I error rate of 5%, 100 subjects, 50 allocated to the DASH/SRD-control diet sequence and 50 allocated to the controlDASH/SRD diet sequence, provides >80% power to detect an effect

size (mean treatment difference/standard deviation) of 0.22 and >90% power to detect an effect size of 0.26. This sample size provides >80% power to detect an effect size of 0.5 in cfPWV change between salt-sensitive vs. salt-resistant subjects. This is a between-groups comparison based on a two-sample t test and two-sided Type I error of 5%.

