The remainder of the outcomes are *Phase 2*-related, i.e. intended to determine longer-term effects of dietary change between the WHEELS and non-WHEELS groups, with both receiving motivational interviewing-based dietary counseling. The primary outcome of *Phase 2* was the change in left ventricular mass index (LVMI, using the Devereaux and Dubois formulas for left ventricular mass and body surface area, respectively) by echocardiography, with secondary outcome of change in PWV, between baseline and end of study participation. These outcomes were assessed using linear regression adjusted for baseline value. Key additional pre-specified outcomes were the change in DASH/SRD adherence measured both by 3-day food diary and Food Frequency Questionnaire (FFQ) and the change in clinic systolic and diastolic blood pressure (BP), between baseline and end of study participation. These were measured using generalized estimating equations to account for repeated within-subject measures over time (baseline/2 weeks and at 1 and 6 months of *Phase 2*) and interaction with WHEELS treatment group assignment. Other pre-specified outcomes were changes in serum triglycerides and urine sodium:potassium ratio between baseline to the end of study, evaluated using 2-sample t-testing.

The sample size for *Phase 2* was set by the participants completing *Phase 1* and influenced by drop-out during the 6 months of the interventions to promote DASH/SRD adoption. We assumed that an additional 10% of subjects will drop out during *Phase 2*, resulting in 90 subjects with evaluable data. The sample size was estimated based on anticipated effects on DASH/SRD adherence, the presumed primary driver of cardiovascular and BP changes in the study. Based on national survey data and our preliminary work, we expected the mean baseline DASH/SRD adherence score by 3-day food diary to be 2.5 ± 1.5 points (scale, 0-9). A sample size of 90 provides >80% power to detect an intra-group change of 0.6 between baseline and the end of study, based on paired t-testing two-sided Type I error of 5%. This sample size provides >80% power to detect a differential between group change in dietary score of 0.9, based on a two-sample t test and two-sided Type I error of 5%.

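### The SAP's single Phase 2 primary (BSA-indexed LVMI, WHEELS versus non-WHEELS) conflicts with the protocol's two Phase 2 primaries, with no reason given and no LVMI effect justified for that contrast

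*SAP*

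**What the plan says.** **Protocol.** Two outcomes are called primary for Phase 2.

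- *Diet.* Under Phase 2 study design and Phase 2 Sample size and power, the Aim 2 primary is the change in DASH/SRD concordance score from the Block FFQ, WHEELS-I versus motivational interviewing alone.
- *Cardiovascular.* Under Phase 2 study design, the primary cardiovascular outcome is the change in LVMI from Week 2 to month 6, indexed to height^2.7. The contrast is by salt sensitivity. The Phase 2 Introduction hypothesises that "sustained adoption of the DASH/SRD over 6 months will produce greater improvement in structural cardiovascular HFpEF risk factors in salt-sensitive than salt-resistant subjects", and the sample-size section powers that comparison. Study procedures takes left ventricular mass from 3D echocardiographic images.

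**SAP.** Phase 2 outcomes are "intended to determine longer-term effects of dietary change between the WHEELS and non-WHEELS groups, with both receiving motivational interviewing-based dietary counseling". The one Phase 2 primary "was the change in left ventricular mass index (LVMI, using the Devereaux and Dubois formulas for left ventricular mass and body surface area, respectively"), analysed by linear regression adjusted for baseline. The diet score has a lower rank: "Key additional pre-specified outcomes were the change in DASH/SRD adherence measured both by 3-day food diary and Food Frequency Questionnaire (FFQ"). Salt-sensitivity groups appear only for Phase 1. On power, the SAP says: "The sample size was estimated based on anticipated effects on DASH/SRD adherence, the presumed primary driver of cardiovascular and BP changes in the study".

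**The concern.** LVMI is a primary in both documents, but its index, its method for mass and its comparison groups all differ, so the two documents estimate different quantities. The randomised question of Aim 2, whether WHEELS improves diet, is still analysed but is no longer primary. The protocol's primary cardiovascular question has no described Phase 2 analysis.

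The index is not a cosmetic detail. Body surface area depends on weight; height^2.7 does not. The protocol (Phase 2, Potential problems/alternative approaches) accepts that some participants may lose weight. With left ventricular mass unchanged, weight loss would raise LVMI/BSA and leave LVMI/height^2.7 where it was.

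Two things are at stake. The Phase 2 primary conclusion would rest on a contrast for which neither document states an expected effect. And the SAP is dated May 31, 2025, opens with "The study was conducted in two phases" and mentions participant flow. Without dates and reasons, a reader cannot tell whether the primary changed before or after results by group were known.

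**Working it through.** **1. The two plans side by side**

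| Item | Protocol | SAP |
|---|---|---|
| Diet score | Aim 2 primary, FFQ, by WHEELS arm | Key additional, food diary and FFQ |
| LVMI index | height^2.7 | Body surface area (Dubois) |
| LV mass | 3D images | Devereaux formula |
| LVMI contrast | Salt-sensitive vs salt-resistant | WHEELS vs non-WHEELS (by the framing sentence) |
| Phase 2 power | Diet score and LVMI | Diet score only |
| Reason for difference | – | None stated |

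**2. The stated power figures reproduce**

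Inputs from Phase 2 Sample size and power: 90 evaluable, taken as 45 versus 45; two-sided 5%; two-sample t test.

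- LVMI at 0.6 SD: noncentrality = 0.6 × sqrt(45/2) = 2.85, power 80.4%. The stated figure is >80%.
- Diet score at 0.9 points, taking 1.5 as the SD of change: 0.9/1.5 = 0.60 SD, power again 80.4%. The stated figure is >80%.
- LVMI in units, with the protocol's SD of change of 4 to 7 g/m^2.7: 0.6 × 4 = 2.4 and 0.6 × 7 = 4.2, as stated.

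**3. What carries over to the SAP's contrast**

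Half the participants are randomised to WHEELS-I, so 45 versus 45 applies there too and the arithmetic transfers. The justification does not. The protocol argued for 0.6 SD as a fall in salt-sensitive participants against no change in salt-resistant ones. Both WHEELS arms receive counselling, and neither document gives an expected LVMI difference between them, or an SD in g/m^2.

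**4. What the WHEELS contrast can show** (noncentral t, 45 versus 45)

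The detectable effect at 80% power is 0.597 SD. The smaller effects below are assumptions.

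| True difference in LVMI change | Power |
|---|---|
| 0.2 SD | 16% |
| 0.3 SD | 29% |
| 0.4 SD | 47% |
| 0.6 SD | 80% |

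The SAP adjusts for baseline, which multiplies the residual SD by sqrt(1 − r²). With an assumed baseline–change correlation r of 0.3 or 0.5, the detectable effect becomes 0.57 or 0.52 SD.

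The unadjusted 95% CI half-width is t(0.975, 88) × sqrt(2/45) = 1.987 × 0.2108 = 0.419 SD. On the protocol's scale that is 0.419 × 4 = 1.7 to 0.419 × 7 = 2.9 g/m^2.7. An estimate of zero would exclude 0.6 SD but not effects smaller than about 0.42 SD.

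**5. Two primaries at 5% each**

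If independent: 1 − 0.95² = 0.0975, or about 9.8%, for at least one false positive.

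**6. The baseline diet score of 2.5 ± 1.5**

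- Protocol, Phase 2 Sample size and power: a Week 2 baseline value, given in connection with the FFQ-based primary.
- Protocol, Figure 8: food diary but no FFQ at Week 2; FFQ at screening and Month 6.
- Protocol, Phase 1 Dietary intervention: baseline FFQ assessment is described under the Week 2 visit.
- SAP: "we expected the mean baseline DASH/SRD adherence score by 3-day food diary to be 2.5 ± 1.5 points".

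These four places do not agree on instrument and visit.

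**The case against.** **The SAP may simply prefer randomised groups.** It says that because Phase 1 "occurred prior to randomization, the comparator groups are salt-sensitive and non salt-sensitive individuals". This hints at why Phase 2 is framed by randomised arm, and a randomised contrast has real merit. It does not explain the new index and mass method, the lower rank of the diet score, or the missing Phase 2 salt-sensitivity analysis.

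**Diet is the presumed driver, so powering on diet is reasonable.** That explains the sample-size basis. It gives no size for the LVMI effect and no reason for preferring LVMI to diet as primary.

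**The primary was switched after results were seen.** A reader might infer this from the date and tense. The documents do not show it. The protocol's title page is not available for this review, so its version date cannot be compared, and the SAP calls several other Phase 2 outcomes pre-specified. The change may have been made and documented in time, in which case relabelling the primaries now would itself be a late change. Restoring the protocol's primaries should therefore depend on the answer.

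**The SAP moved 2.5 ± 1.5 from one instrument to another.** The protocol is itself ambiguous here, and the SAP may be resolving that ambiguity. What stands is that the places need reconciling.

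**The SAP does not expressly withdraw the salt-sensitivity analysis.** True. It is a short document, and its silence is not a cancellation. But a reader following it would not know that the analysis is still planned, or with what rank.

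**Conclusion.** The conflict is real and should be resolved before the Phase 2 results are relied on. Protocol and SAP disagree on which outcomes are primary, which groups are compared for LVMI, and how LVMI is measured and indexed, and no reason is given.

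This is not a power error: every figure checked reproduces. The gap is that the SAP's primary has no effect size, SD or power of its own. At 45 versus 45 it has 80% power for about 0.60 SD, an effect that neither document argues for between two counselled arms. Power is 29% if the true difference is 0.3 SD, which is an assumption. The calculations rest on 90 evaluable participants split equally, and the conversion to g/m^2.7 rests on the protocol's SD of 4 to 7. No conversion to g/m^2 is possible from the documents.

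The documents do not support a finding of results-driven switching. They support only that a reader cannot rule it out.

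**What to change.** In the Phase 2 part of the SAP:

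1. List each difference from the protocol (primary outcome, contrast, LVMI index and mass method, diet instrument). For each, state when and why it was made and whether results by group had been seen.
2. Unless the change is documented as made before results by group were seen, keep the protocol's two primaries:
   - change in FFQ DASH/SRD score by WHEELS arm;
   - change in LVMI/height^2.7, with mass from 3D images, by the salt-sensitivity definition in Phase 1 study design (24-hour mean BP change of at least 8 mmHg).

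   Then present LVMI/BSA with Devereaux mass as a sensitivity analysis, LVMI and PWV by WHEELS arm as secondary without a power claim, and the weight-change-adjusted analyses that the protocol promises.
3. In either case, report both sets of analyses, labelled, and state that the two protocol primaries at 5% each carry no joint error control (about 9.8% if independent).
4. State which instrument and visit 2.5 ± 1.5 refers to, and make the protocol and SAP agree.

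**Cost.** SAP wording, a table of differences and a small amount of extra analysis and reporting, on data the protocol already collects (FFQ, height, weight, echocardiography, 24-hour BP). The downside is that LVMI by WHEELS arm may become secondary.

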Sample size and power: The sample size is based on a combination of logistical considerations and power required to detect important differences in the primary endpoint of change in cfPWV in the context of a randomized crossover design. Sample size is based on a 2-sequence, 2-period, 2-treatment crossover design for continuous endpoints (using paired t test for mean differences). We conservatively assume a within-subject correlation of 0.70 for cfPWV measurements, based on our DASH-DHF pilot (0.81) and literature showing same-day correlation >0.90 (Wimmer et al. 2007) using the Sphygmocor device. We also assume approximate 10% dropout rate during Phase 1 of our study. Under these assumptions and using a two-sided type I error rate of 5%, 100 subjects, 50 allocated to the DASH/SRD-control diet sequence and 50 allocated to the control-DASH/SRD diet sequence, provides >80% power to detect an effect size (mean treatment difference/standard deviation) of 0.22 and >90% power to detect an effect size of 0.26. For comparison purposes, the effect size of cfPWV changes with DASH/SRD in our preliminary work in HFpEF has been 0.4-0.6; in dietary sodium restriction studies in healthier populations than we plan to study, the effect size is at least 0.2-0.4 (Seals et al. 2001, Todd et al. 2010). This sample size provides >80% power to detect an effect size of 0.5 in cfPWV change between salt-sensitive vs. salt-resistant subjects. This is a between-groups comparison based on a two-sample t test and two-sided Type I error of 5%.

Analysis plan: We will examine the distributions of outcomes under each treatment (e.g., DASH/SRD and control diet), as well as by salt-sensitive phenotype. Graphical approaches such as boxplots and scatterplots will be used, allowing identification of outliers, linearity, and correlation of measurements within subject and across time. If the distributional assumptions of our models are not met, transformations will be employed.

Obvious outliers unrelated to data entry error will prompt reconfirmation of acquisition methods and quality by another blinded investigator. We expect no carryover effects due to the two week duration of each dietary segment, a sufficient interval to match sodium intake and excretion even in subjects with chronic kidney disease (McMahon et al. 2013), who have more difficulty achieving this balance.

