**Phase 2 study design:** We will test our working hypotheses by providing motivational interviewing-based counseling to all participants and randomizing half to the WHEELS-I program, with both interventions described further below. The primary outcome of Aim 2 of this proposal, to be tested in Phase 2 of the protocol, is the intra- and inter-group mean change in DASH/SRD concordance score (Mellen et al. 2008) from the baseline value obtained at the beginning of the study. This score provides 1 point for fully meeting each of 9 DASH/SRD targets and 0.5 for meeting an intermediate level of each target (e.g. fiber 14.8 g and 9.5g/1000 kcal, respectively). The secondary dietary outcome is the group change in mean 24-hour urinary sodium excretion compared to baseline values. Other outcomes of interest are urinary potassium, microalbuminuria, and the nutrient composition from three day food diaries.

We will also test if DASH/SRD adoption differentially improves HFpEF-associated structural cardiovascular parameters in salt-sensitive vs. salt-resistant subjects (as they were defined by BP response in *Phase 1*). The primary cardiovascular outcome of *Phase 2* is the change from baseline (Week 2 visit) to 6 months in left ventricular mass index (LVMI, indexed to height2.7). This measure was chosen because LVMI is a strong risk factor for incident HF (Gottdiener et al. 2000), can decrease after 6 months of dietitian-counseled sodium restriction (Jula et al. 1994, Liebson et al. 1995), and is relevant to the pathophysiology of HFpEF (Melenovsky et al. 2007). Key secondary outcomes include cfPWV (see *Aim 1*), left atrial volume, indexed for body surface area (LAVI) (Melenovsky et al. 2015), and 24-hour mean BP.

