Phase 2 data collection: History and exam, questionnaires, blood tests, 24-hour BP and urine collections will be performed at months 1 and 6 of Phase 2 (see Study procedures above). Dietary concordance with DASH/SRD, the measure of exposure in Phase 2, will be assessed via Block Food Frequency Questionnaire and 24-hour urine sodium excretion at month 6, and 3-day food diaries immediately prior to the Month 1 and Month 6 visits. Arterial tonometry, echocardiography, SDF microscopy, and the mini-SBT will be performed at Month 6 of Phase 2 (see also Figures 7 and 8). Following Phase 2, participants will have follow-up after 6 months via telephone interview to assess cardiovascular events and vital status; subjects will be mailed a Food Frequency Questionnaire to evaluate persistence of dietary patterns after study participation; and there may be an optional in-person visit determined by study staff, based on need, for an additional arterial tonometry procedure and blood pressure check.

Dietary intervention: Phase 2 of the protocol will begin within 2 weeks of the end of Phase 1, and typically will begin immediately (i.e., as part of the week 4 visit). During this period, participants will be placed back on their prior antihypertensive therapy, if any, under [name] guidance. Prior to the first Phase 2 visit, subjects will be randomized to control (motivational interviewing only) or the addition of the WHEELS-I program. At the first visit of Phase 2, participants will update their cognitive representation of the DASH/SRD, and have an inperson dietitian session during which motivational interviewing techniques will be employed to explore and support willingness to change dietary habits. If the participant desires, the motivational interviewing portion of the visit may be conducted by telephone. Motivational interviewing-based counseling will continue via telephone during week 2, month1 visit, and at months 2 and 4.

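### The Phase 2 LVMI and PWV regressions adjust for one baseline reading although a second, pre-randomisation reading is scheduled at Week 4; precision is lost, by an amount the documents do not fix

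*SAP*

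**What the plan says.** In its Phase 2 paragraph the SAP names the change in LVMI as primary and the change in PWV as secondary for WHEELS versus non-WHEELS, and says of both: "These outcomes were assessed using linear regression adjusted for baseline value". It does not say which visit supplies that value for these two outcomes. The protocol (Study Phase 2, study design) does so for LVMI: "change from baseline (Week 2 visit) to 6 months in left ventricular mass index".

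A second reading is scheduled. The protocol's Figure 8 marks arterial tonometry and echocardiography at Week 2, Week 4 and Month 6. The SAP describes Phase 1 "with outcomes assessed at 2 and 4 weeks of study participation", and its Phase 1 secondary outcome is a change in strain "by echocardiography, between week 2 and week 4 of study participation". After Phase 1 the two outcomes are next measured at the end of Phase 2: "Arterial tonometry, echocardiography, SDF microscopy, and the mini-SBT will be performed at Month 6 of Phase 2".

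On order, the SAP says that Phase 1 "of the study occurred prior to randomization". The protocol (Study Phase 2, Dietary intervention) is less definite: "Prior to the first Phase 2 visit, subjects will be randomized to control" or WHEELS-I, and that first visit usually forms part of the Week 4 visit.

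**The concern.** Any measurement taken before allocation may be used as a covariate in a randomised comparison without biasing it. Here every participant goes through usual diet and then provided DASH/SRD meals before Phase 2. Feeding can therefore change how well Week 4 predicts Month 6, but it cannot favour one arm.

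Both outcomes are noisy, and about 90 people are expected to be evaluable. A second reading that explains more of the Month 6 variation would narrow the interval for the WHEELS effect without any new data. This matters more because the SAP gives no power for LVMI or PWV in the randomised comparison. The protocol's LVMI power statement concerns salt-sensitive versus salt-resistant participants.

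**Working it through.** **The plan's own figure.** The protocol claims more than 80% power for a 0.6 SD difference in LVMI change with 90 participants split 45:45 at two-sided 5%. The standard error is √(2/45) = 0.211 SD; 0.6/0.211 = 2.846; 2.846 − 1.960 = 0.886; power is 81.2% (80.4% with the exact t distribution). The figure reproduces, but it is for the salt-sensitivity contrast. Neither document states an efficiency figure for the covariate-adjusted WHEELS comparison.

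**Inputs.**
- Within-subject correlation for carotid-femoral PWV: 0.70 assumed, 0.81 in the pilot (protocol, Phase 1, Sample size and power). Both are short-interval values.
- Correlation of either outcome from Phase 1 to Month 6: not given. The values 0.4-0.8 below are assumptions.
- Within-subject correlation for LVMI: not given. The protocol gives only an SD of change of 4 to 7 g/m^2.7.
- Evaluable participants: 90 (both documents).

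**Formulas.** Let a be the Week 2-Week 4 correlation, and b2 and b4 the correlations of Week 2 and Week 4 with Month 6. With Week 2 in the model, analysing change or the Month 6 value gives the same arm effect. As a share of total variance, the residual is:
- Week 2 only: 1 − b2².
- Both as separate covariates: 1 − (b2² + b4² − 2·a·b2·b4)/(1 − a²).
- Proportional reduction: (b4 − a·b2)² / [(1 − a²)(1 − b2²)].

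If all three correlations equal ρ, the reduction is ρ²/(1 + ρ)². At ρ = 0.70 the residual goes from 1 − 0.49 = 0.510 to 1 − 0.98/1.70 = 0.424, a fall of 17.0%. The standard error is multiplied by √0.830 = 0.911, which is 8.9% smaller and equivalent to 90/0.830 ≈ 108 participants.

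| a | b2 | b4 | Week 2 only | Both | Variance fall | SE fall |
|---|---|---|---|---|---|---|
| 0.70 | 0.70 | 0.70 | 0.510 | 0.424 | 17.0% | 8.9% |
| 0.81 | 0.81 | 0.81 | 0.344 | 0.275 | 20.0% | 10.6% |
| 0.81 | 0.70 | 0.70 | 0.510 | 0.459 | 10.1% | 5.2% |
| 0.70 | 0.60 | 0.60 | 0.640 | 0.576 | 9.9% | 5.1% |
| 0.81 | 0.60 | 0.60 | 0.640 | 0.602 | 5.9% | 3.0% |
| 0.70 | 0.50 | 0.50 | 0.750 | 0.706 | 5.9% | 3.0% |
| 0.81 | 0.50 | 0.50 | 0.750 | 0.724 | 3.5% | 1.8% |
| 0.70 | 0.70 | 0.60 | 0.510 | 0.486 | 4.7% | 2.4% |
| 0.70 | 0.60 | 0.50 | 0.640 | 0.627 | 2.0% | 1.0% |
| 0.81 | 0.50 | 0.40 | 0.750 | 0.750 | 0.0% | 0.0% |
| 0.81 | 0.40 | 0.50 | 0.840 | 0.750 | 10.7% | 5.5% |
| 0.70 | 0.70 | 0.80 | 0.510 | 0.322 | 36.9% | 20.6% |

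A simulation of 4,000 trials of 90 participants with equal correlations gave variance falls of about 17% at 0.70 and 19% at 0.81, in line with the first two rows.

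**Separate covariates or an average.** With a = 0.81, b2 = 0.70 and b4 = 0.60, the mean of the two readings leaves 1 − 0.65²/0.905 = 0.533, against 0.510 for Week 2 alone, so averaging raises the variance by 4.5%. Separate covariates cannot lose in this way.

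**Cost.** Residual degrees of freedom go from 90 − 3 = 87 to 86, a variance cost of roughly 1/86, or about 1%.

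**The case against.** The strongest reply is that nothing here is wrong: linear regression adjusted for one baseline value is a standard, unbiased analysis with correct type I error. That stands. A reader might infer that the WHEELS comparison is biased or invalid; the documents give no ground for that.

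A reader might also infer a fixed loss of 11-20% of residual variance for both outcomes, which is what the equal-correlation formula gives for correlations from 0.5 to 0.81. The documents do not support this. Their only correlations are for PWV over a short interval. Antihypertensives other than calcium channel blockers are weaned during Phase 1 and prior therapy is resumed for Phase 2, so Weeks 2 and 4 may resemble each other more than either resembles Month 6. For LVMI every value would be an assumption.

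Week 2 and Week 4 are also not replicates. They follow different diets, and the trial expects individuals to respond differently. This bears on how much Week 4 predicts, not on bias, and it is a reason not to average.

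The timing objection stands in part. On the protocol's wording, allocation could precede the Week 4 measurements. WHEELS-I messages begin only in Phase 2 and cardiovascular readings are analysed blinded to dietary assignment, so any effect is likely to be small, but the order needs confirming.

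Finally, the SAP is dated May 2025 and written in the past tense. It does not say whether outcomes had been seen by arm. Changing the primary model after that would be post hoc.

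**Conclusion.** The point holds as a missed gain in precision. A Week 4 reading of both outcomes is scheduled, is placed before randomisation by the SAP, and is unused in the Phase 2 models. For PWV the residual variance would fall by about 17-20% if correlations of 0.70-0.81 apply across all three visits, by about 3-10% if both visits correlate 0.5-0.6 with Month 6, and by about 0-5% if Week 4 correlates 0.1 less with Month 6 than Week 2 does. If Week 4 tracks Month 6 better by 0.1, the gain is about 11-37%. For LVMI, the Phase 2 primary outcome, the size is unknown. That the addition introduces no bias rests on the Week 4 measurements having preceded allocation.

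**What to change.** In the SAP's Phase 2 paragraph, for WHEELS versus non-WHEELS only:
- State that baseline for LVMI and PWV is the Week 2 visit, and keep the outcome as change from it.
- Enter the Week 2 and Week 4 values as two separate covariates, not their mean.
- Impute a missing Week 4 covariate from other baseline data, without using arm or outcome, so that nobody is dropped.
- Confirm from the trial records that Week 4 echocardiography and tonometry preceded allocation, and reconcile the SAP and protocol wording on this.
- If outcomes have already been examined by arm, keep the one-baseline model as planned and report the two-baseline model as a labelled sensitivity analysis.

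Do not carry the change over to the salt-sensitivity contrast. Those groups are defined by the blood pressure response between Week 2 and Week 4, so the Week 4 value is not a pre-exposure covariate there.

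The cost is one degree of freedom per model and a short addition to the SAP; no new data are needed.
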